10.7. Appendix 7: Abbreviations

The following is a list of abbreviations that may be used in the protocol.

Abbreviation	Term
ADE	adverse device effect
ADL	activity/activities of daily living
AE	adverse event
AESI	adverse event of special interest
Al(OH) ₃	aluminum hydroxide
ALT	alanine aminotransferase
ARI	acute respiratory illness
AST	aspartate aminotransferase
AxMP	auxiliary medicinal product
BP	blood pressure
CAP	community-acquired pneumonia
CBER	Center for Biologics Evaluation and Research (United States)
CFR	Code of Federal Regulations (United States)
CHF	congestive heart failure
CI	confidence interval
CIOMS	Council for International Organizations of Medical Sciences
CK	creatinine kinase
CONSORT	Consolidated Standards of Reporting Trials
COPD	chronic obstructive pulmonary disease
CpG	cytosine phosphate guanine
CRF	case report form
CRO	contract research organization
CSR	clinical study report
CTIS	Clinical Trial Information System
DCT	data collection tool
DILI	drug-induced liver injury
DNA	deoxyribonucleic acid
DU	dispensable unit
EC	ethics committee
ECG	electrocardiogram or electrocardiography
eCRF	electronic case report form
EDB	exposure during breastfeeding
EDMC	external data monitoring committee
EDP	exposure during pregnancy
eICD	electronic informed consent document
EMA	European Medicines Agency
eSAE	electronic serious adverse event

Abbreviation	Term
EU	European Union
EudraCT	European Union Drug Regulating Authorities Clinical Trials (European Clinical Trials Database)
FDA	Food and Drug Administration (United States)
FSH	follicle-stimulating hormone
GBS	Guillain-Barré syndrome
GCP	Good Clinical Practice
GGT	gamma-glutamyl transferase
GMFR	geometric mean fold rise
GMT	geometric mean titer
HBe	hepatitis B e
HBeAg	hepatitis B e antigen
HBsAg	hepatitis B surface antigen
HBV	hepatitis B virus
HCAP	healthcare-associated pneumonia
HCV	hepatitis C virus
HIV	human immunodeficiency virus
HRSV	human respiratory syncytial virus
IB	investigator's brochure
ICD	informed consent document
ICH	International Council for Harmonisation of Technical Requirements for Pharmaceuticals for Human Use
ICU	intensive care unit
ID	identification
ILI	influenza-like illness
IM	intramuscular
IMP	investigational medicinal product
IND	investigational new drug
INR	international normalized ratio
IP	Internet Protocol
IPAL	investigational product accountability log
IPM	investigational product manual
IRB	institutional review board
IRT	interactive response technology
ISO	International Organization for Standardization
IV	intravenous(ly)
LB	lower bound
LFT	liver function test
LLOQ	lower limit of quantitation
log e	natural logarithm
LRTD	lower respiratory tract disease

Abbreviation	Term
LRTI	lower respiratory tract illness
LRTI-RSV	RSV-associated lower respiratory tract illness
MDR	medical device regulation
MedDRA	Medical Dictionary for Regulatory Activities
MFDS	Ministry of Food and Drug Safety (Republic of Korea)
MHRA	Medicines and Healthcare products Regulatory Agency (United Kingdom)
mITT	modified intent-to-treat
MQI	medically qualified individual
N/A	not applicable
NDCMC	newly diagnosed chronic medical condition
NI	noninferiority
NIMP	noninvestigational medicinal product
NT	neutralizing titer
PACL	protocol administrative change letter
PFS	prefilled syringe
PI	principal investigator
PSSA	Pfizer's Serious AE Submission Assistant
PT	prothrombin time
qRT-PCR	quantitative reverse transcription–polymerase chain reaction
QTL	quality tolerance limit
RCDC	reverse cumulative distribution curve
RNA	ribonucleic acid
RSV	respiratory syncytial virus
RSV A	respiratory syncytial virus subgroup A
RSV B	respiratory syncytial virus subgroup B
RSVpreF	respiratory syncytial virus stabilized prefusion F subunit vaccine
RT-PCR	reverse transcription–polymerase chain reaction
SADE	serious adverse device effect
SAE	serious adverse event
SAP	statistical analysis plan
SD	standard deviation
SIIV	seasonal inactivated influenza vaccine
SmPC	summary of product characteristics
SoA	schedule of activities
SOP	standard operating procedure
SRSD	single reference safety document
SUSAR	suspected unexpected serious adverse reaction
TBA	to be announced
T bili	total bilirubin
UADE	unanticipated adverse device effect

Abbreviation	Term
ULN	upper limit of normal
US	United States
USADE	unanticipated serious adverse device effect
USPI	United States prescribing information
VE	vaccine efficacy
WHO	World Health Organization
WOCBP	woman/women of childbearing potential

1. VERSION HISTORY

Table 1. Summary of Changes

Version/ Date	Associated Protocol Amendment	Rationale	Specific Changes
1 12 Aug 2024	Original 05 Apr 2024	N/A	N/A

2. INTRODUCTION

This SAP provides the detailed methodology for summary and statistical analyses of the data collected in Study C3671053.

2.1. Modifications to the Analysis Plan Described in the Protocol

There is no change in analysis from the plan specified in the protocol.

2.2. Study Objectives, Endpoints, and Estimands

Type	Objective	Endpoint	Estimand
Primary Safety	To describe the safety profile of RSVpreF when administered to Korean adults ≥ 60 years of age	
 Local reactions (redness, swelling, and pain at the injection site) Systemic events (fever, fatigue, headache, vomiting, nausea, diarrhea, muscle pain, and joint pain) AEs SAEs NDCMCs 	In participants receiving the study intervention, the percentage of participants reporting: 
 Local reactions within 7 days after vaccination Systemic events within 7 days after vaccination AEs within 1 month after vaccination SAEs throughout the study NDCMCs throughout the study
Primary Immunogenicity	To describe the immune responses to RSV A and RSV B elicited by RSVpreF in Korean adults ≥ 60 years of age	
 RSV A and RSV B serum NTs 	In participants in compliance with the key protocol criteria (evaluable immunogenicity population): 
 GMT of NTs for RSV A and RSV B at each blood sampling visit GMFR of NTs for RSV A and RSV B from before vaccination to 1 month after vaccination
Secondary Immunogenicity	To further describe the immune responses to RSV A and RSV B elicited by RSVpreF in Korean adults ≥ 60 years of age	
 RSV A and RSV B serum NTs 	Seroresponse ^a rate of NTs for RSV A and RSV B at 1 month after vaccination

a. Seroresponse is defined as a postvaccination NT ≥ 4 times the LLOQ if the baseline titer is below the LLOQ; or a ≥ 4 -fold rise from baseline to after vaccination if the baseline titer is \geq LLOQ.

2.2.1. Primary Estimand(s)

2.2.1.1. Immunogenicity Primary Estimand(s)

The primary estimands for the RSV immunogenicity objective will use the hypothetical strategy to describe the RSVpreF immune response in participants without the intercurrent events. In other words, the immune response is estimated in the hypothetical setting where participants follow the study schedule and protocol requirements as directed. It includes the following 5 attributes:

- **Treatment condition:** RSVpreF or placebo group as randomized at Visit 1.
- **Population:** Older adults in Korea, as defined by the study inclusion and exclusion criteria.
- **Variables:** RSV A and RSV B serum NTs.
- **Intercurrent events:** The following intercurrent events could impact the interpretation or the measurement of the immune response:
 1. The participant did not meet the study inclusion criteria or did meet the exclusion criteria.
 2. The participant did not receive the study intervention as randomized.
 3. Major protocol violations: The participant received a prohibited vaccine or treatment that may alter the immune response.
 4. Blood was taken outside an acceptable window for immunogenicity evaluation (<27 days or >42 days after RSVpreF administration).

The clinical question of interest is the immune response elicited from RSVpreF, without any influence from any other immune-modifying drugs or vaccines and measured at a homogeneous time window. Therefore, all data after Intercurrent events 1, 2, and 3, as well as all data at Intercurrent event 4, if collected, will be excluded. Major protocol violations will be determined by clinical review.

- **Population-level summary:** GMT of NTs before vaccination and 1 month after vaccination and GMFR of NTs from before vaccination to 1 month after vaccination, per study intervention group.

2.2.1.2. Safety Primary Estimand(s)

2.2.1.2.1. Reactogenicity Estimand(s)

The primary estimands for the safety objective will use the treatment policy strategy and estimate the safety rate, regardless of whether an intercurrent event occurs.

Reactogenicity estimands have the following 5 attributes:

- **Treatment condition**: RSVpreF or placebo received on Day 1.
- **Population**: Participants as defined by the study inclusion/exclusion criteria.
- **Variables**: Each item included in the e-diary from Days 1 through 7 after vaccination (refer to [Section 3.1.2.1](#)).
- **Intercurrent events**: All data collected after the intercurrent events will be included.
- **Population-level summary**: The rates of reporting each reactogenicity item in each treatment/intervention condition.

2.2.1.2.2. Adverse Event Estimand(s)

The AE estimands have the same attributes (treatment condition, population, and intercurrent events) as the reactogenicity estimands (Section 2.2.1.2.1), except:

- **Variables**: Any AE reported within 1 month after vaccination ([Section 3.1.2.2](#)).
- **Population-level summary**: The rates of the variable (any AE reported within 1 month after vaccination) in each treatment condition.

2.2.1.2.3. Serious Adverse Event Estimand(s)

The SAE estimands have the same attributes (treatment condition, population, intercurrent events, and population-level summary) as the AE estimands (Section 2.2.1.2.2), except:

- **Variables**: Any SAE reported throughout the study ([Section 3.1.2.2](#)).

2.2.1.2.4. Newly Diagnosed Chronic Medical Condition Estimand(s)

The NDCMC estimands have the same attributes (treatment condition, population, intercurrent events, and population-level summary) as the AE estimands (Section 2.2.1.2.2), except:

- **Variables**: Any NDCMC reported throughout the study ([Section 3.1.2.2](#)).

2.2.2. Secondary Estimand(s)

2.2.2.1. Secondary Immunogenicity Estimand

The secondary immunogenicity estimand has the same attributes (treatment condition, population, and intercurrent events) as the primary immunogenicity estimand (Section 2.2.1.1), except:

- **Variables:** Seroresponse of NTs for RSV A and RSV B (Section 3.2).
- **Population-level summary:** Seroresponse rate for RSV A and RSV B per study intervention group at 1 month after vaccination.

2.2.3. Additional Estimand(s)

Additional estimands, as supplementary analyses to support the immunogenicity objective(s) (Section 2.2.1.1 and Section 2.2.2.1), are defined. Treatment policy will be used to address intercurrent events, which are listed in Section 2.2.1.1 for the immunogenicity objective(s). The remaining 4 estimand attributes (treatment condition, variables, population, and population-level summary) are the same.

2.3. Study Design

This is a Phase 3, randomized, double-blinded, placebo-controlled, multicenter trial to describe the safety, tolerability, and immunogenicity of bivalent RSVpreF in adults 60 years of age and older in Korea. Approximately 360 study-eligible participants will be randomized to receive either the 120- μ g dose of RSVpreF or placebo in a 2:1 ratio. Randomization will be stratified by 3 age groups (60 through 69, 70 through 79, and \geq 80 years), with approximately 100 participants estimated to be enrolled in the 70- through 79-year and \geq 80-year age strata combined. All participants will have blood drawn at baseline prior to vaccination and at 1 month after vaccination to assess immunogenicity.

Prespecified local reaction and systemic event data will be collected in an e-diary during the 7-day collection period, or longer for ongoing symptoms, after study intervention (ie, from Day 1, the day of vaccination, until symptom resolution). Reported Grade 3 and potential Grade 4 reactogenicity events will be assessed by the investigator or qualified person to determine unscheduled medical visit requirements.

For all participants, AEs will be collected from informed consent through 1 month following study intervention administration. SAEs, NDCMCs, and AESIs will be collected from informed consent throughout study participation.

~360 Healthy adults ≥60 years of age randomized 2:1	Visit 1 (Day 1) Vaccination	Visit 2 1-Week Follow-Up Telephone Call 7-13 Days After Vaccination	Visit 3 1-Month Follow-Up Blood Draw 28-35 Days After Vaccination	Visit 4 2-Month Follow-Up Telephone Call 56-70 Days After Vaccination
Study Groups				
Group 1 RSVpreF n = 240	 			
Group 2 Placebo n = 120	 			
Safety				
Local reactions and systemic events ^a	Days 1 to 7 after vaccination 			
AEs	Informed consent to Month 1 			
AESIs SAEs NDCMCs	Informed consent to Month 2 			
 Immunogenicity blood draw  Study intervention administration  Telephone contact for safety data				

a. Collected for 7 days, or longer for ongoing symptoms, after study intervention until symptom resolution.

3. ENDPOINTS AND BASELINE VARIABLES: DEFINITIONS AND CONVENTIONS

3.1. Primary Endpoint(s)

3.1.1. Immunogenicity Primary Endpoints

RSV A- and RSV B-neutralizing antibody titers will be determined on sera collected before vaccination and at the 1-month postvaccination visit.

RSV A and RSV B serum NTs at each blood sampling time point are included in the assay result data, thus no derivation is needed. The following variables will be derived for each participant:

1. RSV A and RSV B serum NTs at each blood sampling time point: This will be derived as the geometric mean of RSV A and RSV B NTs measured at each blood sampling time point for each participant.
2. RSV A, RSV B, and RSV A/B NT fold rise: This will be derived from NTs after vaccination to before vaccination. The numerator is the NT value 1 month after vaccination and the denominator is the NT value before vaccination.

Titers above the LLOQ are considered accurate and their quantitated values will be reported. Refer to [Section 5.3.2](#) for LLOQ details. Titers below the corresponding LLOQ, denoted as BLQ, will be set to $0.5 \times \text{LLOQ}$ for analysis. Missing assay results will not be imputed.

When calculating a fold rise, if assay results are $< \text{LLOQ}$, the assay results will be converted to $0.5 \times \text{LLOQ}$, except when the prevaccination assay result is $< \text{LLOQ}$ while the postvaccination result is $\geq \text{LLOQ}$, in which case the prevaccination value will be set to the LLOQ.

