9. STATISTICAL CONSIDERATIONS

Detailed methodology for summary and statistical analyses of the data collected in this study is outlined here and further detailed in the SAP, which will be maintained by the sponsor. The SAP may modify what is outlined in the protocol where appropriate; however, any major modifications of the primary endpoint definitions or their analyses will also be reflected in a protocol amendment.

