9.3. Statistical Analyses

The SAP will be developed and finalized before any analyses are performed and will describe the analyses and procedures for accounting for missing, unused, and spurious data. This section is a summary of the planned statistical analyses of the primary and secondary endpoints.

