9.3.1. General Considerations

Unless stated otherwise, “vaccine group” in this section refers to the study intervention group. CIs for all endpoints in the statistical analysis will be presented as 2-sided at the 95% level unless specified otherwise.

The safety analyses are based on the safety population. Participants will be summarized by vaccine group according to the study interventions they received. Missing AE dates will be handled according to the Pfizer safety rules.

For all the immunogenicity endpoints, the analysis will be based on the evaluable immunogenicity population. An additional analysis may be performed based on the mITT immunogenicity population if there is a large enough difference in sample size between the mITT immunogenicity population and the evaluable immunogenicity population. Participants will be summarized according to the vaccine group to which they were randomized. Missing immunogenicity results will not be imputed. Immunogenicity results that are below the LLOQ will be set to $0.5 \times \text{LLOQ}$ in the analysis; this may be adjusted once additional data on the assay characteristics become available.

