9.3.1.2.2. Geometric Mean Fold Rises

Fold rises are defined as ratios of the results after vaccination to the results before vaccination. The calculations of fold rises are limited to participants with nonmissing values at both time points.

GMFRs will be calculated as the mean of the difference of logarithmically transformed assay results (later time point minus earlier time point) and exponentiating the mean. The associated 2-sided 95% CIs will be obtained by constructing CIs using the Student t distribution for the mean difference on the logarithm scale and exponentiating the confidence limits.

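### Does the SAP's below-LLOQ rule for fold rises, which SAP 2.1 does not list as a change from the protocol, require a change to the plan?

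*SAP*

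**What the plan says.** **Protocol.** Section 9.3.1 gives one rule for all immunogenicity endpoints: "Immunogenicity results that are below the LLOQ will be set to" 0.5 × LLOQ, with the rider that "this may be adjusted once additional data on the assay characteristics become available". Section 9.3.1.2.2 defines the fold rise as the post/pre ratio in participants with both values and adds no separate LLOQ handling. The GMFR from baseline to 1 month is a primary estimand (protocol Section 3).

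**SAP.** Sections 3.1.1 and 5.3.2 keep 0.5 × LLOQ as the general rule and make one exception for fold rises. When the baseline alone is below the LLOQ, "in which case the prevaccination value will be set to the LLOQ". A below-LLOQ postvaccination value stays at 0.5 × LLOQ, and if both values are below, both are converted alike. Section 2.1 states: "There is no change in analysis from the plan specified in the protocol".

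**Division of labour.** Protocol Section 9 says "The SAP may modify what is outlined in the protocol where appropriate", but that "any major modifications of the primary endpoint definitions or their analyses will also be reflected in a protocol amendment". Protocol 9.3 describes itself as a summary and says the SAP "will describe the analyses and procedures for accounting for missing, unused, and spurious data".

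**The concern.** Taken literally, the three statements conflict: the protocol has no exception for fold rises, the SAP has one, and the SAP says nothing has changed. The quantity affected is a primary estimand in a study meant to support licensure in Korea.

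A reader who relied on the protocol and SAP 2.1 would recompute the GMFR with 0.5 × LLOQ and could miss the reported value. The reported GMFR could also differ from the ratio of the two GMTs in the same paired participants, because the GMTs keep 0.5 × LLOQ. Protocol 9.5 does not say which rule produced its historical GMFR of about 10, so comparison with that figure would be slightly unclear if anyone crosses the LLOQ.

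The exception is also one-sided. Upward crossings are treated differently and downward ones are not. In a placebo arm with no true change, that would pull the GMFR slightly below 1.

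**Working it through.** **1. Which participants differ.** Take an illustrative LLOQ of 50.

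| Pre / post | Protocol rule | SAP 3.1.1 and 5.3.2 |
|---|---|---|
| 100 / 1000 | 10 | 10 |
| 30 / 400 | 400/25 = 16 | 400/50 = 8 |
| 100 / 30 | 25/100 = 0.25 | 0.25 |
| 30 / 30 | 1 | 1 |

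Only the upward crosser changes, and that fold rise is halved. The two SAP sections agree in all four patterns.

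**2. Effect on the GMFR.** The GMFR is exp(mean log fold rise), and each upward crosser loses ln 2. So GMFR(SAP) = GMFR(protocol) × 2^-p, with no assumption about distributions. With n = 210 (protocol 9.5), one crosser lowers the GMFR by 1 − 2^(-1/210) = 0.33%.

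This holds for RSV A and RSV B separately. For the combined RSV A/B fold rise in the SAP, a participant who crosses on one antigen only would shift by (ln 2)/2 if the exception is applied per antigen, so the factor does not carry over directly.

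**3. Size for RSVpreF.** p is not in the documents, and SAP 5.3.2 leaves the LLOQs to the released assay data. Assumed range: 0 to 10%. The 95% CI half-width on the log scale is t(209) × SD/√210, which is 0.150 at SD 1.1 (RSV A) and 0.163 at SD 1.2 (RSV B). The shift is p × ln 2.

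| p | GMFR, if 10 under the protocol rule | Shift as share of half-width |
|---|---|---|
| 0 | 10.00 | 0 |
| 1% (about 2 of 210) | 9.93 | 4–5% |
| 5% (10–11 of 210) | 9.66 | 21–23% |
| 10% (21 of 210) | 9.33 | 42–46% |

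**4. The plan's own figure.** Protocol 9.5 gives a 2.4% (RSV A) and 5.0% (RSV B) probability that the CI lower bound falls below 7.5. Using its rounded log values, the difference is 2.3 − 2.0 = 0.3. A noncentral t with 209 df and noncentrality 0.3/(SD/√210) gives 2.42% and 4.99%, so the figures reproduce.

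Suppose the historical value of about 10 came from the 0.5 × LLOQ rule (not stated) and the SD is unchanged. Replacing 0.3 by 0.3 − p ln 2 then gives 2.98% and 5.90% at p = 1%, and 6.43% and 10.94% at p = 5%. The SD would in fact move a little. Under a normal model with a baseline/fold-rise correlation from 0 to −0.7 (assumed), the p = 5% values run from about 5% to 7% for RSV A and 9% to 11% for RSV B.

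For scale, using the unrounded ln(10/7.5) in place of 0.3 already gives 3.5% and 6.7% at p = 0. That is a larger move than p = 1% produces.

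**5. Placebo with no true change.** If baseline and 1-month titers are exchangeable, the protocol rule centres the GMFR at 1 and the SAP rule at 2^-u, where u is the upward-crossing share: 1.000 at u = 0, 0.993 at 1% and 0.979 at 3% (u assumed).

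**6. Agreement with seroresponse.** For a below-LLOQ baseline, SAP 3.2 and protocol Section 3 require a post titer of at least 4 × LLOQ. Under the SAP fold-rise rule, post/LLOQ ≥ 4 is the same condition. Under the protocol rule, post/(0.5 × LLOQ) ≥ 4 needs only 2 × LLOQ. A participant between 2 and 4 × LLOQ would then show a fourfold rise and still be a non-responder.

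**The case for a change.** The strongest case for acting is that permission to modify does not make a statement of no change true. The protocol rider ties any adjustment to new assay data, and the SAP cites none. Listing the exception in SAP 2.1 would take one sentence, and a table of crossing counts would show whether p is zero. The literal mismatch, and the point about the rider, stand.

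The rest carries less weight.

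- The authority for the SAP rule does not depend on the rider. Protocol Section 9 lets the SAP modify the plan generally and reserves amendments for major changes. Substitution for one pattern of censored pairs, with the GMFR estimator, population and visits untouched, can reasonably be judged not major.
- To be misled, a reader would have to skip both SAP sections that state the exception.
- SAP version 1 is tied to the original protocol of 05 Apr 2024, whereas the protocol available is Amendment 1. The visible part of the change log lists nothing for Section 9, but that part is incomplete. Whether the declaration was inaccurate when written therefore cannot be settled from these documents.
- Reverting to 0.5 × LLOQ would remove the one-sidedness at the price of the seroresponse mismatch in step 6. That is a trade-off, not a clear gain.
- Crossing counts and a GMFR under the other rule would be informative extras, but no test, success criterion or between-group GMFR contrast depends on them.

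**Conclusion.** The texts do differ and the factor 2^-p is exact, but no change to the plan follows. An analyst who follows the SAP has one unambiguous rule, set in advance, that can only lower the RSVpreF GMFR or leave it alone, and that agrees with the seroresponse definition. GMTs and seroresponse rates are the same under either rule. Protocol 9.1 rules out hypothesis testing, and the 7.5 in protocol 9.5 is not a success criterion.

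The difference is nil if nobody crosses upward, 0.7% of the GMFR at p = 1% and 3.4% at p = 5%. Those shares are assumptions. The shifts in the 9.5 probabilities also need an unstated historical rule, and the placebo figures need an assumed crossing share; both are illustrative only. What is left is an omission in the declaratory sentence of SAP 2.1, and correcting it would alter no reported number.
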